4.8.1 Analysis of biological samples

4.8.1.1 Clinical chemistry samples

The analyte stability limits defined by the contracted central clinical laboratory will be applied to all analyses performed on behalf of AstraZeneca. The central laboratory will not analyse samples that fall outside these stability limits. Analytical data will not be reported if found to have been derived from a sample that fell outside these stability limits. The standards of procedure followed by the central laboratory may be amended in accordance with its Standard Operating Procedures. The central laboratory will inform AstraZeneca of the stability limits relevant to this study before the first patient gives informed consent to take part in the study.

If the contracted central clinical laboratory chooses to sub-contract the analytical work to another laboratory, the contracted central clinical laboratory must assure itself and provide assurance to AstraZeneca that the other laboratory will apply defined stability limits to all analyses performed on behalf of AstraZeneca. Samples falling outside these limits must not be analysed or data reported. The other laboratory will inform AstraZeneca of the stability limits relevant to this study before the first patient gives informed consent to take part in the study.

4.8.1.2 Pharmacokinetic samples

The long-term stability of the analyte(s) will be documented in method validation reports produced by AstraZeneca and Bristol-Myers Squibb. Results from analyses of samples stored longer than the time period for which stability has been demonstrated should not be reported unless complementary analyte(s) stability data is acquired and amended to the relevant method validation report.

4.9 Genetic measurements and co-variables

Patients who provide written informed consent related to genetic research will provide a blood sample according to the Study Plan, see Table 1. Individual patients will not be identified. Samples and data will be kept confidential and stored separately. For more information, see Appendix F.

5. DATA MANAGEMENT

Data must be entered into the WBDC system at the investigational centre within 2 business days after the scheduled visit (except for SAEs that should be entered within 1 calendar day). Trained study personnel will be responsible for entering data into the WBDC system according to the Instructions for the Investigator including the data entry instructions. Data includes observations, tests and assessments specified in the protocol. Data entered in the WBDC system will immediately be saved at a central database and changes tracked to provide an audit trail. When data has been entered, reviewed, edited and Source Data Verification

(SDV) performed, the Investigator will electronically sign the eCRF and the data will be locked to prevent further editing. A copy of the eCRF will be provided to the investigational centre after the study database has been locked for archiving at the investigational centre.

Data from the central laboratory assessments will be returned to AstraZeneca directly as datasets, and validated to ensure that it is consistent with the clinical data. Any queries on the data will be raised and resolved within the WBDC system or other designated systems.

Data verification and validation will be performed. The Investigator should answer any external queries raised by AstraZeneca in a timely manner, and query resolutions will be saved in the central database. Prior to breaking the treatment codes at Week 52 and separately at Week 104, all decisions on the evaluability of the data from each individual patient must have been made and documented. The Study Delivery Team at AstraZeneca R&D will document the date of clean file and database lock.

The Study Data Management Plan will describe in greater detail the methods used to collect, check, and process clinical data. It will also clarify the roles and responsibilities of the various functions and personnel involved in the data management process.

Following database lock, required amendments to the database due to critical errors will only be allowed with the appropriate supporting documentation. Non-critical errors will not result in amendments to the database but will be captured via the appropriate documentation. An electronic copy (disc or equivalent) of the eCRF will be made available to the Investigator centre after the study database has been locked.

Concomitant medications will be coded using the Bristol-Myers Squibb Drug Dictionary. AEs will be coded using MedDRA.

6. STATISTICAL METHODS AND DETERMINATION OF SAMPLE SIZE

6.1 Statistical evaluation – general aspects

All statistical evaluation, as well as summaries and tabulations and the pharmacokinetic evaluation will be done by qualified personnel at AstraZeneca and Bristol-Myers Squibb. The pharmacokinetic data derived from this study may be pooled with similar data from other studies and the results described in a separate report. Before breaking the treatment codes for Week 52 and separately for Week 104 analyses, all decisions on the evaluability of the data from each individual patient at end of both Study Period C and D will be made and documented and each patient will be assigned to the appropriate analysis data set.

A comprehensive Statistical Analysis Plan (SAP) for both study periods C and D will be prepared before unblinding of the Week 52 and Week 104 data.

6.2 Description of outcome variables in relation to objectives and hypotheses

The primary objective of this study is to assess whether saxagliptin plus metformin is non-inferior (NI) to glipizide (sulphonylurea) plus metformin in improving glycaemic control in patients with type 2 diabetes. The primary outcome variable is the change from baseline in HbA1c at 52 weeks of treatment.

When evaluating NI of saxagliptin plus metformin against glipizide plus metformin, the null hypothesis is the mean of the saxagliptin plus metformin in question is inferior to the mean of the glipizide plus metformin in question by a fixed amount or more (the NI limit) with respect to absolute change from baseline in HbA1c at Week 52 of treatment. Per Committee for Proprietary Medicinal Products (CPMP) scientific discussion, a NI limit of 0.35% for change from baseline has been selected for comparisons against glipizide add-on to metformin. Assay sensitivity can be achieved if the attainment of 0.6% in HbA1c reduction from baseline at Week 52 (Section 3.2.1.2) is observed from the glipizide add-on to metformin treatment arm.

The key secondary outcome variables at Week 52 are:

- Proportion of patients reporting at least one episode of hypoglycaemic event over 52 weeks, a safety outcome variable.
- Change from baseline in body weight at Week 52, a safety outcome variable.
- Mean slope of the regressions of change from Week 24 in HbA1c on treatment duration after Week 24.

The above three secondary variables (proportion of patients reporting at least one episode of hypoglycaemic events, change from baseline in body weight and mean slope of the regressions of change from baseline in HbA1c on treatment duration after Week 24) have been identified for special consideration in this study, in addition to the primary efficacy variable (NI HbA1c). Multiple comparisons procedure will be applied in order to control the type I error rate to support secondary superior claims of saxagliptin plus metformin treatment over glipizide plus metformin therapy. When evaluating superiority of saxagliptin add-on to metformin to glipizide add-on to metformin with respect to each of the above secondary endpoints, the hypotheses and statistical methods are:

- 1. Hypoglycaemic event: the null hypothesis is the equality of the two proportions of patients with at least one hypoglycaemic event against the alternative hypothesis of the inequality of the two proportions of patients with at least one hypoglycaemic event. Fisher's exact test will be used to compare the association of two proportions with the treatment on the safety analysis set.
- 2. Change from baseline to Week 52 in body weight: The null hypothesis is the equality of the two mean weight changes from baseline to Week 52 against the alternative hypothesis of the inequality of the two mean weight changes are not

equal. Analysis of covariance model (ANCOVA) method will be used on safety analysis set, where mean changes from baseline to Week 52 will be the response variable and the model will include treatment as a fixed effect and baseline weight as a covariate.

3. Durability: the null hypothesis is the equality of the two mean slopes against the alternative hypothesis of the inequality of the two slopes. Student's t-test will be use on patients who have HbA1c levels recorded for Week 24 and at least a second one recorded on or before Week 52. Missing values will not be imputed for visits between Week 24 and Week 52.

Other secondary efficacy variables are:

- Change from baseline in FPG, insulin, C-peptide, glucagon and proinsulin.
- Proportion of patients achieving a therapeutic glycaemic response defined as HbA1c ≤6.5%.
- Change from baseline in HbA1c in patients with baseline HbA1c \geq 7.0%.
- Proportion of patients achieving a therapeutic glycaemic response defined as HbA1c < 7.0% in patients whose baseline HbA1c is $\ge 7.0\%$.
- Change from baseline in β -cell function (as measured by HOMA-2 (Wallace et al 2004)).
- Change from baseline in AUC from 0 to 180 minutes for glucose, insulin, C-peptide and glucagon during an OGTT on a subset of patients.
- Change from baseline in insulinogenic index (Phillips et al 1994)) on a subset of patients.
- Change from baseline in insulin sensitivity as measured by OGIS (Mari et al 2001) and Matsuda Index (Matsuda and DeFronzo 1999) on a subset of patients.
- Change from baseline in TC, LDL-C, HDL-C and TG.

Data analysis for population pharmacokinetics will be outlined in a separate analysis plan and the results will be reported in a separate report.

Safety and tolerability will be evaluated by assessment of adverse events (including AEs of special interest, such as oedema and skin-related AEs, and hypoglycaemic events), laboratory values, ECG, pulse, blood pressure, body weight and physical examination. No hypotheses are proposed a priori for these safety-related variables.

Tertiary endpoints at Week 104 are:

To compare the long-term safety, tolerability and efficacy effects of saxagliptin versus glipizide given as add-on therapy to metformin after a 104-week double-blind treatment period, assessed as those identified for the Week 52 period, except the evaluations are for the entire 104 weeks.

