Durability of HbA1c will be assessed for each of the two treatment groups from mean slopes of the regressions of change from Week 24 in HbA1c on treatment duration from Week 24 to Week 52. All patients with a pair of HbA1c levels at Week 24 and post Week 24 will be included. Weeks on randomized treatment period will be used as a regressor. Only observed values between the two visits, inclusive, will be used for the analysis.

For the safety endpoints, the data set utilized will be the safety analysis set, which will include observed data only. This data set will include patients who have taken at least one dose of double-blind investigational product.

For all changes (or percent changes) from baseline to a specific time point post-baseline for the primary and secondary efficacy, analysis will be based on the per protocol analysis set. These analyses will be supplemented by using the full analysis set.

Three secondary variables (proportion of patients reporting hypoglycaemic events, change from baseline in body weight and mean slope of the regressions of change from baseline in HbA1c on treatment duration after Week 24) have been identified for special consideration in this study, in addition to the primary efficacy variable (non-inferior (NI) HbA1c). In order to control overall type 1 error rate of the study, a fixed-sequence test will be adopted with respect to the four hypotheses, ie, the testing will be sequentially performed for non-inferiority comparison of HbA1c, superiority tests for hypoglycaemic event and then weight changes and mean slope for durability. All comparisons will be two-sided at the 5% significance level.

TABLE OF CONTENTS

PAGE

	TITLE PAGE	1
	PROTOCOL SYNOPSIS	2
	TABLE OF CONTENTS	9
	LIST OF ABBREVIATIONS AND DEFINITION OF TERMS	14
1.	INTRODUCTION	17
1.1	Background	17
1.2	Rationale	18
2.	STUDY OBJECTIVES	18
2.1	Primary objective	18
2.2	Secondary objectives	18
2.3	Tertiary objectives	19
3.	STUDY PLAN AND PROCEDURES	20
3.1	Overall study design and flow chart	20
3.2 3.2.1	Rationale and risk/benefit assessment	
	study population	
3.2.1.1	Study design and regulatory requirement	
3.2.1.2 3.2.1.3	Study doses and control groups	
3.2.1.4	Choice of study population	
3.2.2	Risk/benefit and ethical assessment	
3.3	Selection of study population	32
3.3.1	Study selection record	
3.3.2	Inclusion criteria	32
3.3.3	Exclusion criteria	33
3.3.4	Restrictions	
3.3.5	Discontinuation of patients from treatment or assessment	35

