3.3.5.2 Procedures for discontinuation

Patients who discontinue should always be asked about the reason(s) for their discontinuation and the presence of any AEs. If possible, they should be seen and assessed by an investigator(s). AEs should be followed up; diary cards and investigational products should be returned by the patient.

Patients discontinuing due to an AE will be asked to provide a blood sample for assessment of plasma concentrations (see section 4.5.1) at the next visit in conjunction with completion of other protocol specified procedures. In addition, the time of last intake of study medication along with an accurate time of obtaining the blood sample should be recorded.

Patients with an increased serum creatinine will have their metformin held and a repeated serum creatinine test within one week. If this repeated serum creatinine still is increased, despite temporary coexisting contributing factors have been overcome, the patient should discontinue the clinical study.

Randomized patients in the Randomized treatment period (Period C) who do not complete the entire study should complete the procedures described for Visit 13 (end of Period C). Randomized patients in the Extension period (Period D) who do not complete the entire study should complete the procedures described for Visit 17 (end of Period D).

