6.3.4 Full analysis set last observation carried forward (LOCF)

For the analysis of all Week 52 efficacy endpoints, the full analysis set is a subset of randomized analysis set including patients who take at least one randomized investigational product dose, have non-missing baseline and a post baseline efficacy data. The missing Week 52 efficacy endpoints will be replaced by last observed value after baseline. Missing baseline (Visit 3) data will be estimated by a single value assessed at Visit 1, if one exists. Analysis of efficacy variables at Week 52 will be supplemented by the results from the full analysis set.

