6.3.5 Safety analysis set

The safety analysis set is a subset of randomized analysis set including patients who take at least one IP dose and have any safety records that can be found in the study database. Actual

treatment will be re-assigned to any patient who has taken IP dose other than what they were randomized to for the duration of the entire 52 weeks. Analysis will only use values that are actually measured.

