6.4 Method of statistical analysis

6.4.1 Analysis of double-blind treatment Period C

The primary efficacy analysis to establish non-inferiority with 0.35% non-inferiority limit on the change in HbA1c from baseline to Week 52 will be performed on a per protocol analysis set using ANCOVA. The model will use treatment group as a fixed effect and baseline value as a covariate. Within the framework of the ANCOVA model, point estimates and the two-sided 95% confidence intervals for the mean change within each treatment group as well as for the differences in mean change between the saxagliptin plus metformin treatment arm and the glipizide plus metformin treatment arm will be performed. Saxagliptin plus metformin will be considered not inferior to glipizide plus metformin if the upper limit of the two-sided 95% confidence interval of the difference in change in HbA1c from baseline to Week 52 between saxagliptin plus metformin and glipizide plus metformin is less than 0.35%.

Analyses of the secondary efficacy endpoints will be performed using ANCOVA methods for change from baseline in glucose related endpoints, β -cell functions, and insulin sensitivity. The ANCOVA model will use treatment group as a fixed effect and baseline value as a covariate. Within the framework of the ANCOVA model, point estimates and the two-sided 95% confidence intervals for the mean change within each treatment group as well as for the differences in mean change between the two treatment groups will be reported.

Repeated measures analysis may be performed on selected efficacy variables over time as sensitivity analysis.

Hypoglycaemic events and body weight changes are considered as safety variables and are specified as important secondary variables supporting the treatment of saxagliptin. Proportion of patients reporting at least one episode of hypoglycaemic event over the 52-week treatment period will be compared between the two treatment groups using a two-sided Fisher's exact test. ANCOVA method comparing the two treatment groups will be used for change from baseline in body weight at Week 52, where the model will include treatment as a fixed effect and baseline as a covariate.

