Durability of HbA1c will be assessed for each of the two treatment groups from mean slopes of the regressions of change from Week 24 in HbA1c on treatment duration from Week 24 to Week 52. All patients with a pair of HbA1c levels at Week 24 and post Week 24 will be included. Weeks on randomized treatment period will be used as a regressor. Only observed values between the two visits, inclusive, will be used for the analysis.

Three secondary variables (proportion of patients reporting hypoglycaemic events and change from baseline in body weight, and mean slopes of the regressions of change from baseline in HbA1) have been identified for special consideration in this study, in addition to the primary efficacy variable (NI HbA1c). In order to control overall type 1 error rate of the study, a fixed-

sequence test will be adopted with respect to the 4 hypotheses, ie, the testing will be sequentially performed in the following order:

- 1. Non-inferiority comparison of HbA1c, if NI is demonstrated then statistical inference proceed step 2, otherwise inference will stop.
- 2. Superiority tests for hypoglycaemic event if significant (p<0.05) in favour of saxagliptin and metformin treatment group then statistical inference proceed step 3, otherwise inference will stop.
- 3. Superiority test for weight changes, if significant (p<0.05) in favour of saxagliptin and metformin treatment group then statistical inference proceed step (4), otherwise inference will stop.
- 4. Superiority inference for durability.

All comparison will be two-sided at the 5% significance level.

All other secondary efficacy variables are supplemental and not included in the multiple comparison scheme as outlined above.

Summary tables will be presented for proportions of patients achieving glycaemic therapeutic response.

Change from baseline in AUC from 0 to 180 minutes for glucose, insulin, C-peptide and glucagon will be analyzed by ANCOVA method similar for the primary endpoint. The lipid endpoints will be log-transformed before ANCOVA analysis. In which case log baseline will be used as a covariate and treatment as a fixed effect in the model. Within the framework of the ANCOVA model, point estimates and the two-sided 95% confidence intervals will be first constructed in the logarithmic scale. By taking the anti-logarithms, estimates and confidence intervals for the true geometric means and ratios of true geometric means will be displayed.

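### The confirmatory body-weight test uses only patients with a measured Week 52 weight and ignores eight earlier scheduled weights, although discontinuation is tied to glycaemic response

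*Protocol*

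**What the plan says.** **The test.** Protocol section 6.2 states for weight: "Analysis of covariance model (ANCOVA) method will be used on safety analysis set, where mean changes from baseline to Week 52 will" be the response, with treatment as a fixed effect and baseline weight as covariate. Section 6.4.1 and the synopsis give the same model.

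**The data rule.** Section 6.3.5 says of the safety set: "Analysis will only use values that are actually measured". The synopsis says of the safety endpoints that "the data set utilized will be the safety analysis set, which will include observed data only".

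**Its role.** Section 6.4.1 makes this step 3 of 4: "Superiority test for weight changes, if significant (p<0.05) in favour of saxagliptin and metformin treatment group". Success opens the durability test.

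**What covers missing data elsewhere.** Section 6.3.4: "The missing Week 52 efficacy endpoints will be replaced by last observed value after baseline". Section 6.4.1: "Repeated measures analysis may be performed on selected efficacy variables over time as sensitivity analysis". Section 6.3 adds a full-set analysis for efficacy endpoints. Section 6.4.1 places weight outside that class: "Hypoglycaemic events and body weight changes are considered as safety variables".

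**Leaving early.** Section 3.3.5.1 lists discontinuation for confirmed high FPG at Weeks 3, 12, 18 and 24, for HbA1c above 8.0% at Weeks 30 and 39, and for major or recurring minor hypoglycaemia. Under section 3.3.5.2, randomized Period C patients "who do not complete the entire study should complete the procedures described for Visit 13 (end of Period C").

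**The concern.** The safety set nominally holds every treated patient. A Week 52 response combined with an observed-values rule nevertheless fits the model only to patients who have a Week 52 weight. Who those patients are depends on events after randomization, and the protocol's own criteria tie leaving to glycaemic failure and to hypoglycaemia. Section 3.2.1.3 expects saxagliptin to carry a low risk of hypoglycaemia and perhaps to lower weight, so the arms may lose patients for different reasons. Randomization does not protect a comparison restricted to those who remain.

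At stake is a multiplicity-controlled superiority claim, and with it access to the durability test. As the protocol stands, that claim has less protection against missing data than the secondary efficacy endpoints that sit outside the multiplicity scheme.

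**Working it through.** **1. The plan's own figure.** The protocol gives no sample size or power for weight. Its only calculation (section 6.5) is for HbA1c: 838 randomized, about 35% excluded from the per-protocol set, SD 1.1, margin 0.35, true difference 0, power 95%.

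- Evaluable: 838 × 0.65 = 544.7, matching the stated 544, or 272 per arm.
- Standard error: 1.1 × √(2/272) = 0.0943.
- Power: Φ(0.35/0.0943 − 1.96) = Φ(1.75) = 0.96, against 0.95 stated. The figure is reproduced.

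The 35% covers every reason for per-protocol exclusion. Section 6.3.3 names prohibited medication, non-compliance and major deviations as well as non-completion. Patients excluded for those other reasons can still have a Week 52 weight, so 35% is an upper bound on the withdrawal implied by the plan.

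**2. Weights collected and weights used.** Table 1 marks weight after baseline (Visit 3) at Visits 4, 6, 7, 8, 9, 10, 11, 12 and 13, that is Weeks 3, 9, 12, 15, 18, 24, 30, 39 and 52. Eight of these nine precede Week 52. The specified ANCOVA uses only the ninth.

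**3. Do the other provisions reach weight?**

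| Provision | Scope in the protocol | Covers weight? |
|---|---|---|
| LOCF, section 6.3.4 | Week 52 efficacy endpoints | No |
| Full-set analysis, section 6.3 | efficacy endpoints | No |
| Repeated measures, section 6.4.1 | selected efficacy variables, optional | No |

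**4. Precision.** If a share p of patients has no Week 52 weight, the standard error relative to complete data is √(1/(1 − p)). At the upper bound p = 0.35 this is √(1/0.65) = 1.24. A mixed model on the earlier weights would recover only part of this.

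**5. Bias.** Let p be the share without a Week 52 weight in an arm, and d the mean weight change of withdrawn patients minus that of completers. The mean over all patients is the completer mean plus p·d. The completer analysis therefore shifts the saxagliptin-minus-glipizide difference by

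−(p_S·d_S − p_G·d_G).

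The documents give neither p nor d. Assume p from 20% to 40% and d from 0 to −1 kg:

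- p = 0.35 and d = −1 in both arms: −(−0.35 + 0.35) = 0.
- p = 0.35 in both arms, d_S = 0, d_G = −1: −(0 + 0.35) = −0.35 kg.
- p_S = 0.30, p_G = 0.40, d_S = 0, d_G = −1: −(0 + 0.40) = −0.40 kg.
- p_S = 0.40, p_G = 0.30, d_S = −1, d_G = 0: −(−0.40 − 0) = +0.40 kg.

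The shift is therefore between −0.4 and +0.4 kg in this range, in either direction, and zero when the arms match. The bound takes d to have the same sign in both arms; with opposite signs the two terms would add.

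**6. Can the earlier weights help in principle?** An illustrative simulation assumed a true Week 52 difference of −2 kg, a between-patient SD of 4 kg, measurement noise of 1 kg and 200,000 patients per arm.

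- Withdrawal unrelated to weight (about 34% and 33%): the completer estimate was −2.00.
- Withdrawal depending on the last observed weight change, in opposite directions by arm (about 39% in each): completer −0.34, LOCF −1.38, regression imputation from the earlier weights (missing at random) −2.01.

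The second case is deliberately extreme and is built so that missing at random holds. It shows the mechanism and says nothing about the size to expect in this trial.

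**The case against.** The strongest reply is that nothing here shows the conclusion would change. Weight is a secondary safety variable, tested only after HbA1c non-inferiority and hypoglycaemia have succeeded. No discontinuation criterion is based on weight, and the hypoglycaemia criterion applies only after down-titration and contributing factors have been considered. A model using weight alone satisfies missing at random only so far as earlier weights carry the dependence on glycaemia. All of this stands. It limits the size of the point and is a real limit of the remedy. It does not make the present test preferable: the observed-case ANCOVA needs missingness to be unrelated to outcome given treatment and baseline weight, which is a stronger condition than allowing it to depend on earlier weights as well.

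A second reply is that section 6.1 promises a comprehensive SAP. A reader might infer that no analysis anywhere keeps withdrawn patients, and the documents do not support that, because the SAP is not shown and may add a sensitivity analysis. What stands is that the main analysis of a confirmatory hypothesis is fixed in the protocol and has not been left to the SAP.

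A reader might also infer that a weight taken at premature withdrawal enters as a Week 52 value, because it is collected under Visit 13 procedures. The protocol does not say so. Section 3.3.5.2 governs which procedures are done, and Table 3 windows Visit 13 at 52 weeks ±5 days. Assigning such visits is commonly SAP content, so this needs clarification only.

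**Conclusion.** The point holds as a cheap improvement. On the protocol's text, the step-3 superiority test rests on patients with an observed Week 52 weight, while discontinuation is related to treatment response and eight collected weights are left out.

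It is tempting to read this as a bias of known sign, for instance one favouring saxagliptin, or as a stated number of kilograms. The documents support neither, since they give no weight SD, expected effect or withdrawal rate by arm. The 0.4 kg figure rests wholly on the assumed ranges in the working. The factor of 1.24 rests on treating the whole per-protocol exclusion as withdrawal, and is a ceiling.

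**What to change.** In sections 6.2 and 6.4.1 and the synopsis:

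- Make the step-3 test a mixed model for repeated measures on the safety set, using all scheduled on-treatment weights from Week 3 to Week 52, with treatment-by-visit and baseline-by-visit terms. Test the treatment contrast at Week 52.
- State that a weight taken at premature withdrawal is assigned to its actual study week.
- Keep the observed-case Week 52 ANCOVA as a sensitivity analysis.

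The cost is protocol and SAP wording, with no new visits, measurements or patients. The downside is reliance on missing at random given earlier weights, which may not fully capture withdrawal driven by glycaemia.
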